5.1.4 AOFAS and SF-36 survey

Standardized and validated surveys to assess patient function and satisfaction. The SF36 has proven useful in surveys of general and specific populations, comparing relative burden of diseases, and in differentiating the health benefits produced by a wide range of different treatments. In this study we will use the SF36 to assess patient's perceptions of their health.

6 STATISTICAL CONSIDERATIONS

The purpose of the study is to compare the results of immediate weight-bearing versus non-weight-bearing after foot and ankle surgery.

It is hypothesized that immediate weight-bearing following foot and ankle surgery would provide better patient satisfaction with functional outcomes compared to non-weight-bearing after foot and ankle surgery.

6.1 Primary Endpoint

The primary outcome measures are the American Orthopaedic Foot and Ankle Society (AOFAS) Ankle-Hindfoot Scale score and the SF-36 Health Survey Score as it pertains to the patient's ankle/foot. These assessments will be given to the patient in the pre-operative and post-operative periods.

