6.4 Statistical Methods

6.4.1 Analysis of Primary Outcome of Interest

All analysis will begin with assessment of the normality of continuous variables using the Kolmogorov-Smirnov test. Normally distributed continuous variables will be reported as means and standard deviations; non-normally distributed data as median and interguartile range. Categorical data will be reported as counts and percentages. The Student's t-test will be used to compare continuous demographic and clinical data between the immediate weight-bearing and non-weight-bearing groups. The chi-square test or Fisher's exact test will be used to compare categorical data between groups. Cronbach's alpha will be used to measure reliability, or internal consistency, of both the Medical Outcomes Study 36-Item Short Form Health Survey (SF-36) and the AOFAS Ankle-Hindfoot Scale survey (AOFAS). Spearman's rank correlation coefficient will be used to assess the relationship between the physical and mental component scores and the eight subdomain scores from the SF-36 and the pain, function and alignment scores of the AOFAS. SF-36 scores and AOFAS scores will be adjusted for patient age, gender, BMI and presence of diabetes mellitus. Nonparametric tests will be used when data breaks the normality assumption. A value of p<.05 on twotailed testing will be considered statistically significant. Statistical analysis will be performed using IBM-SPSS Statistics, version 24.0 (IBM-SPSS Inc., Armonk, NY). Using one-way repeated measures analysis of variance (ANOVA), differences over time in radiographic and advanced imaging parameters will be assessed separately for the immediate weight-bearing and non-weight-bearing groups. Two-way repeated measures ANOVA will be used to assess differences over time in these parameters between the two groups. Tukey's test or Dunn's procedure will be used for post-hoc pairwise comparisons, as indicated.

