Descriptive statistics on the physical and mental component scores and the eight subdomain scores from the SF-36 will be reported for the immediate weight-bearing and non-weight bearing groups. In order to examine differences in SF-36 scores within each group over time, a one-way repeated measures ANOVA will be conducted to determine if the SF-36 scores are significantly different between visits (e.g., screening, post-operative at 6-8 weeks, post-operative at 12 months, and post- operative at 24 months). A two-way repeated measures ANOVA will be conducted to determine if the SF-36 scores are significantly be conducted to determine if the SF-36 scores are significantly be conducted to determine if the SF-36 scores are significantly be conducted to determine if the SF-36 scores are significantly be conducted to determine if the SF-36 scores are significantly be conducted to determine if the SF-36 scores are significantly be conducted to determine if the SF-36 scores are significantly be conducted to determine if the SF-36 scores are significantly different between the two groups for these same visits. Post-hoc pairwise comparisons using Tukey's test or Dunn's procedure will be performed, as indicated.

Descriptive statistics on the pain, function and alignment component scores from the AOFAS will be reported for the immediate weight-bearing and non-weight bearing groups. In order to examine differences in AOFAS scores within each group over time, a one-way repeated measures ANOVA will be conducted to determine if the AOFAS scores are significantly different between visits (e.g., screening, post-operative at 6 – 8 weeks, post-operative at 12 months, and post-operative at 24 months). A two-way repeated measures ANOVA will be conducted to determine if the AOFAS scores are significantly different between visits. Post-hoc pairwise comparisons using Tukey's test or Dunn's procedure will be performed, as indicated.

The chi-square test will be used to examine the frequency of complications during the perioperative and post-operative periods, osseous healing as assessed by both clinical and radiographic evaluation and frequency of soft tissue procedures between the immediate weight-bearing and non-weight bearing groups.

Logistic regression analysis will be performed to assess which patient characteristics and surgical characteristics are associated with higher SF-36 scores and AOFAS scores.

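### AOFAS and SF-36 are both primary, but the plan sets no success rule, deciding SF-36 score or deciding visit, so either the familywise error or the stated 80% power is unassured

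*Combined protocol and SAP*

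**What the plan says.** Section 6.1 names two instruments: "The primary outcome measures are the American Orthopaedic Foot and Ankle Society (AOFAS) Ankle-Hindfoot Scale score and the SF-36 Health Survey Score". On timing it says only that they are completed before and after surgery. Section 6.2, by contrast, places the analysis of the secondary endpoints at the end of follow-up.

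Section 6.4.1 sets one threshold for everything: "A value of p<.05 on twotailed testing will be considered statistically significant". It refers to several SF-36 scores, for example when planning Spearman correlations for "the relationship between the physical and mental component scores and the eight subdomain scores from the SF-36", and names none as decisive. Its repeated-measures ANOVAs ask whether scores are "significantly different between visits (e.g., screening, post-operative at 6-8 weeks, post-operative at 12 months" and 24 months); the two-way SF-36 version asks whether they are "significantly different between the two groups for these same visits". The only multiplicity procedure is this: "Post-hoc pairwise comparisons using Tukey's test or Dunn's procedure will be performed, as indicated". The section also plans a Student's t-test between arms for continuous demographic and clinical data. Its closing paragraph makes the comparison of the two arms the primary focus and procedure-specific analyses exploratory, without naming an instrument, score, visit or model term.

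Section 6.5 says the power rests on the primary endpoints. It then gives one calculation: an independent-samples t-test, two-sided .05, d = 0.40, 100 evaluable per arm, 80% power, plus 15 per arm for loss, making 230.

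**The concern.** Two primary instruments without a success rule leave three readings open.

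- **Either suffices.** Two tests at .05 give a familywise error above 5%.
- **Both are required.** Error is held at 5%, but the chance of success is below the stated 80%.
- **Two separately reported claims.** Per-test error and power stand as stated, but the chance of at least one false claim is not controlled.

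The text does not choose between them. The open SF-36 score and visit widen the choice further.

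This matters in practice. The protocol's own literature review (section 1.2) describes comparisons with no AOFAS difference, an Achilles-repair study in which four domains of a 36-item survey favoured weight-bearing at six weeks, and an ankle-fracture trial with better SF-36 physical and mental components. If this trial produced such a mixture, the plan could not say whether it had succeeded. The control arm is restricted for 6 weeks, so the 6-8 week and 24-month visits also answer different questions. Once outcomes have been seen, a choice among these options is no longer credible.

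**Working it through.** **Inputs.** From section 6.5: d = 0.40, two-sided .05, 100 evaluable and 115 enrolled per arm. From section 6.1: two primary instruments. Assumed, because the documents give no figure: correlation r between the two test statistics of 0, 0.5, 0.7 or 0.9, and a true d of 0.40 on both instruments when power is computed.

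**Step 1: the plan's own figure.** Noncentrality = d × √(n/2) = 0.40 × √50 = 2.83, with 198 degrees of freedom and critical value 1.972. The noncentral t gives 80.4% power, and 100 is the smallest n per arm that reaches 80%. Then 100 + 15 = 115 per arm, 230 in all. The plan's figure reproduces. With all 115 per arm evaluable, single-test power is 85.6%.

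**Step 2: either suffices, each at .05.** Familywise error = 1 − P(|Z1| ≤ 1.96 and |Z2| ≤ 1.96), bivariate normal. At r = 0 this is 1 − 0.95² = 9.75%.

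**Step 3: both required, each at .05.** Joint power = P(both tests significant). At r = 0 and 100 per arm this is 0.804² = 0.646. The other values come from simulated correlated t statistics.

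**Step 4: Holm, 100 per arm, no baseline adjustment.** An instrument succeeds if its p < .025, or if its p < .05 and the other's p < .025.

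| | r = 0 | 0.5 | 0.7 | 0.9 |
|---|---|---|---|---|
| Familywise error, either suffices | 9.75% | 9.1% | 8.35% | 7.0% |
| Joint power, both required, 100 per arm | 65% | 69% | 72% | 75% |
| Joint power, both required, 115 per arm | 73% | 77% | 79% | 81% |
| Holm, power per instrument | 78% | 77% | 76% | 75% |
| Holm, at least one succeeds | 92% | 86% | 82% | 78% |

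**Step 5: what baseline adjustment could return.** Adjusting for the pre-operative score multiplies the outcome variance by 1 − ρ², where ρ is the pre/post correlation (not given in the documents). At 100 per arm and d = 0.40, the ρ needed for 80% is:

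| | r = 0 | 0.5 | 0.7 | 0.9 |
|---|---|---|---|---|
| Holm, per instrument | 0.21 | 0.26 | 0.28 | 0.31 |
| Both required, joint | 0.48 | 0.44 | 0.40 | 0.31 |

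**Step 6 (secondary): why the model term must be named.** This is an illustration only. It assumes compound symmetry, 100 per arm, V = 4 listed visits including screening, and between-visit correlation c of 0.3, 0.5 or 0.7. Group term: effective d = mean effect / √((1 + (V − 1)c)/V). Group-by-visit term: noncentrality = (n/2) × (sum of squared deviations of the visit effects from their mean)/(1 − c), with 3 and 594 degrees of freedom.

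| Effect by visit | Term | c = 0.3 | 0.5 | 0.7 |
|---|---|---|---|---|
| 0, 0.4, 0.4, 0.4 | group | 86% | 76% | 67% |
| 0, 0.4, 0.4, 0.4 | group-by-visit | 68% | 84% | 97% |
| 0, 0.4, 0, 0 | group | 18% | 14% | 13% |
| 0, 0.4, 0, 0 | group-by-visit | 68% | 84% | 97% |

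**The case against.** The strongest reply is that the plan is less open than it looks. Section 6.4.1 makes the comparison of arms primary, its SF-36 ANOVA refers to the two groups, and Tukey or Dunn may limit error within one set of pairwise comparisons. A group-by-visit analysis followed by comparisons at visits is a natural reading. All of that stands, but none of it controls error across the two instruments or selects an SF-36 score, a visit or a success rule.

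Several stronger readings are tempting, and the documents do not support them.

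- *All ten SF-36 scores will be tested.* The two component and eight subdomain scores are listed only for correlation and description; the ANOVA text says just SF-36 scores. The calculation here therefore uses two tests.
- *The t-test in section 6.5 belongs to no planned analysis.* Section 6.4.1 does plan a t-test on clinical data. Whether that includes the scores is unclear, so the fair criticism is that the t-test and the ANOVA are not ranked.
- *The AOFAS ANOVA ignores treatment arm.* The text reads "A two-way repeated measures ANOVA will be conducted to determine if the AOFAS scores are significantly different between visits", but the SF-36 sentence just before it is visibly garbled in extraction, and this one may have lost words too.
- *The 3-month survey has been dropped from analysis.* The visit list is given only as an example.
- *The trial is underpowered.* Step 6 rests on assumed correlations and shows only that the choice of term matters.

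It can also be said that baseline adjustment goes beyond repairing the omission. That is fair: it is an efficiency gain, offered because it can offset the power cost.

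**Conclusion.** The point holds. The arithmetic in section 6.5 is right for one test, but the plan has two primary instruments and no rule joining them. Depending on the reading, familywise error is 7.0% to 9.75% instead of 5%, or joint power at the planned 100 evaluable per arm is 65% to 75% instead of 80%. Reporting two separate claims preserves the per-test figures but not familywise control.

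These sizes rest on an assumed cross-instrument correlation of 0 to 0.9 and, for power, on d = 0.40 for both instruments. The omissions themselves (success rule, SF-36 score, visit) rest on the text alone. The unranked tests and the unnamed ANOVA term are a secondary point. The primary conclusion needs to be fixed before outcome data are examined.

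**What to change.** Before outcome data are examined:

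1. Name one score per instrument (for example the AOFAS total and one SF-36 summary score) and one deciding visit. Label all other scores and visits secondary.
2. State the success rule. If either instrument suffices, use Holm or a fixed sequence. If both are required, keep .05 for each.
3. Make the between-arm difference at that visit the deciding contrast. Section 6.4.1 already says "SF-36 scores and AOFAS scores will be adjusted for patient age, gender, BMI and presence of diabetes mellitus". Add the pre-operative score, which is already collected, to those covariates instead of treating screening as an outcome level.
4. Restate the power in section 6.5 for the chosen rule, without adding patients.

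**Cost.** The statistical plan is part of the protocol, so this is an amendment, and section 6.6 requires protocol changes to go to the IRB. No visits or data are added. The stated power becomes less favourable before baseline adjustment: about 75-78% per instrument under Holm, or 65-75% jointly if both are required. Whether adjustment recovers 80% depends on a pre/post correlation that the documents do not give (Step 5). Under a fixed sequence the first test keeps the full .05, but the second counts only if the first succeeds. An effect confined to another visit becomes secondary evidence.

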6.2 Secondary Endpoints

The secondary outcome measures are the frequency of complications during the perioperative and post-operative periods, osseous healing as assessed by both clinical and radiographic evaluation, and healing outcomes of soft tissue procedures. These results will be analyzed at the end of the follow-up period.

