3.2.1 Duration of Study Participation

The study duration will require 7 visits to the clinic plus a surgery day therefore will require a pre-surgical visit/screening, surgery procedural day and six outpatient post-operative visits to the clinics. The entire follow up period will occur over 2 years.

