6.8 Definition of an Adverse Event

An adverse event is any untoward medical occurrence in a subject who has received an intervention (drug, biologic, or other intervention). The occurrence does not necessarily have to have a causal relationship with the treatment. An AE can therefore be any unfavorable or unintended sign (including an abnormal laboratory finding, for example), symptom, or disease temporally associated with the use of a medicinal product, whether or not considered related to the medicinal product.

All AEs (including serious AEs) will be noted in the study records and on the case report form with a full description including the nature, date and time of onset, determination of non-serious versus serious, intensity (mild, moderate, severe), duration, causality, and outcome of the event.

The risks associated with the study arm, which is immediate weightbearing following foot and ankle surgery include the potential for the following:

- Excessive Pain with weightbearing on the surgical extremity
- Potential wound complications associated with surgical incision sites
- Possible hardware failure
- Possible non-union, mal-union, or delayed union during osseous healing
- Possible non-healing or delayed healing of soft tissue structures

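### The test named for osseous healing is a yes/no chi-square with no scoring visit, no time-to-union analysis and no rule for revised non-unions, so delayed union has no defined place to show

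*Combined protocol and SAP*

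**What the plan says.** Section 6.2 lists among the secondary outcomes "osseous healing as assessed by both clinical and radiographic evaluation, and healing outcomes of soft tissue procedures", and adds "These results will be analyzed at the end of the follow-up period". Section 3.2.1 gives the length: "The entire follow up period will occur over 2 years".

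Section 6.4.1 assigns the test: "The chi-square test will be used to examine the frequency of complications during the perioperative and post-operative periods, osseous healing as assessed" both clinically and radiographically, between the two arms. It also plans analyses of imaging over time: "Using one-way repeated measures analysis of variance (ANOVA), differences over time in radiographic and advanced imaging parameters will be assessed separately" for each arm, and "Two-way repeated measures ANOVA will be used to assess differences over time in these parameters between the two groups". The imaging parameters are not named.

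Section 6.8 includes among the study-arm risks "Possible non-union, mal-union, or delayed union during osseous healing", and section 7.3.2 repeats this. The abstract gives non-union as an example of a complication to be included in the outcomes. Section 7.3.1 names non-union and mal-union for safety monitoring. Neither of these two places names delayed union.

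Table 1 and section 4.3 put imaging at all six post-operative visits (2-3 weeks, 6-8 weeks, and 3, 6, 12 and 24 months). Section 5.1.3 instead makes imaging depend on indication, at visits chosen by the physician.

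**The concern.** Delayed union is a matter of timing. A yes/no healing status shows it only if the status is read early enough, and the plan does not say when it is read. If it is read at the last visit, two things happen in this test. A bone that healed slowly is counted the same as one that healed on time. A non-union that was re-operated and then healed can be counted as a success.

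Both push the arms together on the healing endpoint. The primary objective (section 2.1) would accept results that are similar, so a healing comparison that is insensitive to delay could be read as reassurance about immediate loading. If the scoring visit is left open, it can also be chosen after the data are seen.

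**Working it through.** **The plan's own figure.** Section 6.5 sizes the trial on the questionnaires, with d = 0.40, two-sided 0.05 and 80% power. The normal formula gives n = 2(1.960 + 0.842)² / 0.40² = 98.1, so 99 per arm; the t-test version gives 99.08, so 100. Power at 100 per arm is 80.7% (normal) or 80.4% (t), and 100 + 15 = 115. The figure reproduces, but it says nothing about bone healing, for which no rate or power is stated.

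**Inputs for an illustration.** From the documents: 100 evaluable patients per arm and two-sided 0.05. Assumed, because the documents give no union rates by arm:
- every patient has a bone procedure (optimistic);
- time to union is exponential, with a control median of 1.5, 2 or 3 months;
- the hazard ratio for union is 0.5 or 0.7, meaning slower healing in the study arm.

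**Formulas.** United by month t: control p₁ = 1 − exp(−λt) and study arm p₂ = 1 − exp(−λ·HR·t), with λ = ln 2 / median. Power = Φ[(|p₁ − p₂| − 1.96·se₀) / se₁], where se₀ = √(2p̄(1 − p̄)/n) and se₁ = √((p₁(1 − p₁) + p₂(1 − p₂))/n).

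**Worked case: median 2 months, HR 0.5** (λ = 0.3466)
- 3 months: 64.6% v 40.5% united; se₀ = 0.0706, se₁ = 0.0685; (0.241 − 0.138)/0.0685 ≈ 1.50, so power is 93%.
- 24 months: 99.98% v 98.4% united; se₀ = 0.0125, se₁ = 0.0125; (0.0154 − 0.0245)/0.0125 ≈ −0.73, so power is 23%.

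**Power of a yes/no comparison, by the visit at which status is read**

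| Control median | HR | 3 months | 6 months | 12 months | 24 months |
|---|---|---|---|---|---|
| 1.5 months | 0.5 | 96% | 96% | 64% | 9% |
| 2 months | 0.5 | 93% | 97% | 86% | 23% |
| 3 months | 0.5 | 86% | 96% | 96% | 64% |
| 1.5 months | 0.7 | 50% | 47% | 19% | 4% |
| 2 months | 0.7 | 46% | 52% | 32% | 7% |
| 3 months | 0.7 | 38% | 50% | 47% | 19% |

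The normal approximation is rough near 100% union. Summing exact binomial probabilities over all outcome pairs where the uncorrected test exceeds 1.96 gives, for HR 0.5, 86 to 97% at 3 and 6 months. At 24 months it gives under 1%, 7% and 72% for the three medians. The direction is the same and the 24-month range is wider.

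**Time to union.** With D unions, power = Φ(√(D/4)·|ln HR| − 1.96).
- D = 190 (95% of 200): HR 0.7 gives Φ(2.458 − 1.96) = 69%; HR 0.5 gives over 99%.
- D = 95 (about half the patients having a bone procedure): 41% and 92%.
- Unions needed for 80% power, 4(1.960 + 0.842)² / (ln HR)²: 247 at HR 0.7 and 66 at HR 0.5.

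This formula assumes that union is observed continuously, so a visit-based analysis will have somewhat less power.

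**The case against.** **Other analyses touch bone healing.** A reader might infer that bone healing rests on this single test and that delayed union cannot appear anywhere. The documents do not support that. Section 6.4.1 plans repeated-measures ANOVA of imaging over time between arms, and section 5.1.3 says imaging will evaluate bone healing and fusion. Adverse events are recorded with onset, duration and outcome (section 6.8), so a delayed union could be captured there. What remains is that the ANOVA names no parameter, union status is binary and does not suit that model, and without a definition the recording of delayed union is left to judgement.

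**Revised non-unions are not lost to the trial.** A reader might infer that they vanish from the safety comparison. Non-union is a complication in the abstract, and complication frequency over the whole perioperative and post-operative period has its own chi-square comparison. The problem is confined to the healing endpoint.

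**The timing sentence.** Section 6.2 says when results are analysed, not that healing is scored only at 24 months. It also covers complications, which are plainly counted over the whole period. This is right: final-status scoring is one possible reading, and the defect is that the plan does not choose.

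**The size is assumed.** A reader might infer that the planned test would almost never see a delay. Curves of 97% v 96% at 24 months do give about 5% power (60 to 70 per arm), but that follows from assuming convergence. The 86.36% fusion at 6-8 weeks in section 1.2 cannot anchor the control arm, because those cases had immediate weight-bearing.

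**Time to union is not always the stronger test.** Under such converging curves (86 v 66% at 6-8 weeks, 91 v 77% at 3 months, 95 v 86% at 6 months), a visit-based log-rank test has 48 to 55% power. Chi-square has 75 to 81% at 6-8 weeks, 55 to 63% at 3 months and 40 to 46% at 6 months. This stands, and it is why a fixed early visit should accompany the time-to-union analysis and why a 6-month cut-off alone would be a weak choice.

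**Conclusion.** The concern holds in a limited form. The only test assigned by name to osseous healing is a yes/no chi-square, with no definition of union, no scoring visit, no time-to-union comparison and no rule for revision. A named study-arm risk therefore has no defined place to show, and the rest of the plan does not clearly supply one.

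The consequence is conditional on final-status scoring. In the illustration with hazard ratio 0.5, power falls from 86-97% at 3 to 6 months to 9-64% at 24 months; with hazard ratio 0.7, from 38-52% to 4-19%. Power is reduced, not always nil, and the size rests on assumed exponential healing, assumed medians and a bone procedure in every patient. This is a secondary endpoint, so the gap does not undermine the primary analysis, but it should be closed before the data are examined.

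**What to change.** In sections 6.2 and 6.4.1, for patients with a bone procedure:

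1. Define union and delayed union in advance. The criteria are for the clinical investigators to set.
2. Make the main healing comparison time to union over the scheduled imaging visits, by an interval-censored method. Count a re-operation for healing as failure of first-time union: the patient stays not united from then on, and is not censored at the re-operation.
3. Add the between-arm risk difference with 95% CI for union without revision, at one visit fixed in advance and early enough to show delay.
4. Keep 24-month healing status as descriptive.

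Section 5.1.3 and Table 1 (with section 4.3) disagree on whether imaging is done at every post-operative visit or only where indicated. They must be reconciled, because the time-to-union analysis depends on imaging at known times in both arms.

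The cost is wording, a few derived variables and a little more analysis. No visits are added beyond those in Table 1. The small downside is that the scoring visit must be committed to before the data are seen.
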